This is a single-center, prospective, ‘open-label,’ investigator-initiated pilot study evaluating the role of continuous glucose monitor (CGM) use either alone or with remote monitoring capabilities that enable subjects to share CGM data with family and friends (whom we will call “followers” in this protocol) among women with T1DM associated with pregnancy. We hypothesize that CGM use will decrease percentage of glucose values below the target range, decrease frequency of severe hypoglycemic episodes, and increase post-prandial glucose values into the target range, with a possible reduction in A1C compared to not using CGM during pregnancy. We hypothesize that the use of remote technology (**Share™ technology**) with subject’s designated follower will decrease hypoglycemia fear and the frequency of severe hypoglycemic episodes compared to CGM use alone in pregnancy or not using CGM use in pregnancy. This study aims to improve maternal glucose management among women with T1DM with a hope to also improve health outcomes during pregnancy.

The study will enroll up to 40 patients from the Barbara Davis Center for Childhood Diabetes (BDC) Adult clinic over the age of 18 years who are pregnant (13 weeks gestation or less) or plan to become pregnant within the following 6 months. The study will also attempt to enroll up to 40 followers (one per pregnant subject) who are family members or friends of the pregnant subjects and over the age of 18 years. All subjects meeting these criteria will be invited to sign informed consent and participate in the study. All pregnant subjects will be stratified into one of three groups: (1) CGM use alone, (2) CGM use with Share™, (3) no CGM use. CGM use will be offered to all subjects, but individuals who do not want to wear a CGM will be stratified to Group 3. Stratification for Groups 1 and 2 will depend on the following: subjects and followers who have iPhones, iPads, and/or iPod touches will be placed into Group 2 which requires one of these devices to function, while all others will be placed in Group 1. All subjects will be followed for study visits with similar frequency during the pregnancy, and subjects in Groups 1 and 2 will wear the Dexcom G4 Platinum® CGM system from the first pregnancy visit until delivery. All subjects in Group 2 will also use the Share™ technology from the first pregnancy visit until delivery.

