outcomes over the course of the pregnancy while diabetes control is managed per usual care (Group 1 for women using a non-Dexcom CGM such as Medtronic Enlite CGM or Group 3 for no CGM use). A PRA will maintain an active list of individuals and will update the list continuously as women are assigned into groups. All subjects will have similar clinical visits throughout the pregnancy.

Subjects stratified to Group 2, CGM use with Share™, will be asked to designate followers who will be able to view glucose trends and receive alerts for high or low sensor glucose values on an iPhone, iPad, iPod touch, and/or other compatible device. While multiple followers are allowed, one will be the main follower and will be invited to sign informed consent at the screening visit or within the first two months of each subject's study participation. Subjects stratified into Groups 1 and 3 will be asked to designate a main follower who may be aware of a subject's extreme glucose values (lows or highs) through contact with her and who may intervene on her behalf in such cases and will be invited to sign informed consent at the screening visit or within the first two months of each subject's study participation.

What are the treatment groups?

There will be three 'open-label' treatment arms consisting of routine care in the Pregnancy and Women's Health clinic at the BDC (no CGM use), an intervention arm using the Dexcom G4 or G5 Platinum® CGM system during pregnancy, and an additional treatment arm using the Dexcom G4 or G5 Platinum® CGM system with Share™ remote monitoring capabilities during pregnancy. As this is a non-randomized study and most women will opt to be in the Dexcom alone or Dexcom Share groups, we will include pregnant no CGM users identified through a retrospective chart review into the no CGM arm of the study.

How many subjects per treatment arm?

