A total of up to 40 pregnant women will be prospectively recruited into the study. As this is an 'open-label' study whose group stratification is based on subject characteristics (willingness to wear CGM, subject possession of iPhone, iPad, or iPod touch, follower possession of iPhone, iPad, or iPod touch), we cannot predict the number of subjects per treatment arm. Based on our current pregnant population's willingness to use CGM and device usage, we anticipate that 10 subjects will be in Group 1, 20 subjects in Group 2, and 10 subjects in Group 3. We will include up to 30 additional women in Group 3 identified through a retrospective chart review who were pregnant around the time of study enrollment and before the study began.

In addition, there will one main follower for each prospectively enrolled pregnant subject (up to 40 adults) who will be asked questions once per month about knowledge of the subject's glucose trends and interventions that s/he may have done on her behalf over the last month.

What is the schedule of events for the treatment groups?

After screening, when pregnancy is confirmed subjects will be stratified to Group 1, 2, or 3. Subjects in all groups will have similar study/clinic visits for data acquisition at the screening, pregnancy visits (which occur a minimum of monthly throughout gestation), and post-partum clinic visit. All subjects will be required to test blood glucoses at least 7 times a day throughout pregnancy. All subjects will be asked to log the SMBG values 7 times a day with insulin doses for meals for 1 week every trimester of the pregnancy.

Subjects stratified to CGM wear will be provided with a Dexcom G4 CGM, transmitter, and sensors (4 per month). Subjects stratified to CGM wear who want to use their personal Dexcom G5 devices will be asked to provide Dexcom mobile usernames (if they use G5 with an iPhone) and will be provided with sensors (4

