There will also be a control arm of pregnant patients at the BDC identified through a retrospective chart review who were pregnant around the time of study enrollment or before and who did not use a CGM device throughout their pregnancies. The retrospective chart review will collect data on a subject's medical history, diabetes complications, medications, vital signs, height/weight, A1C, insulin doses, glucose meter downloads, insulin pump downloads (if applicable), and CGM downloads (if applicable) for the most immediate pre-conception visit, all pregnancy visits, and the post-partum visit. Subjects identified through the retrospective chart review will not have filled out any of our questionnaires (baseline, hypoglycemic fear, and postpartum questionnaires), nor will they have had followers who filled out questionnaires. They will not be asked to fill out these questionnaires.

Inclusion Criteria:

Subjects that meet the following criteria will be considered for admission to the study:

1. Signed informed consent before any study-related activities
2. Female aged 18 years and older with T1D duration >1 year
3. Pregnancy with confirmation of gestational age 13 weeks or less
4. Willingness to routinely practice at least 3-7 blood glucose measurements per day
5. Using MDI or CSII therapy
6. Any A1C level
7. Ability and willingness to adhere to the protocol including scheduled study visits for the duration of the pregnancy
8. Able to speak, read, and write English

Exclusion Criteria:

Subjects will be excluded from the study if any of the following apply:

1. Unwilling to sign informed consent and participate in the study
2. Female age 17 years or younger
3. T1D duration <1 year
4. Pregnancy in gestational week 14 or higher
5. Extensive skin changes/diseases that inhibit wearing a sensor on normal skin
6. Severe known allergy to adhesives within the last 3 months
7. Any other condition, as determined by the investigator, which could make the subject unsuitable for the trial, impairs the subject's suitability for the trial, or impairs the validity of the informed consent

Risks and Justification of Procedures:

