CGM: Continuous glucose monitoring is an FDA approved technology that offers a unique and practical way of identifying and differentiating clinical benefits of intensive diabetes care. The American Diabetes Association currently recommends CGM use during pregnancy for high-risk individuals (2). We currently have hundreds of patients, which include many pregnant patients, in the Adult Clinic at The BDC using CGM on a regular basis as part of usual medical management of their diabetes. Subjects may experience pain at the site of sensor insertion. The adhesive pads for the sensor may cause skin erythema for 1 to 2 days or more. An allergic reaction to 1 or more parts of CGM devices may occur which can be mild, moderate, or severe (rare). In rare cases, an infection at the sensor site may occur. In rare cases, the sensor or needle may break inside the body and would require a minor surgical procedure to remove it.

Data Collection Tools:

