All AEs, reported spontaneously by the subject, as well as those noted by the investigator or study staff, regardless of seriousness, severity or expectedness will be recorded on source documents from the time of obtaining the informed consent.

Severe hypoglycemia as defined as a hypoglycemic episode requiring assistance or hospitalization with or without an SMBG is to be reported as an SAE. A hypoglycemic event “requiring assistance” is determined when the subject is unable to treat the event on her own. Any untoward event resulting in hospitalization, extension of hospitalization, death, or threat of death will also be considered an SAE. SAEs will be reported to the DSMB. The endpoints of A1C and mean glucose readings will be excluded from SAE reporting.

Weakness of the Study

This is not a randomized clinical trial, as the Dexcom remote monitoring technology is not available for other types of handheld devices besides the iPhone, iPad, and iPod Touch. This is a pilot study as no one has previously evaluated the role of this mobile technology in diabetes care complicated by pregnancy. Our goal is to learn from this study and plan for a much larger study where handheld devices are also provided and thus randomization can occur in the future after implementing changes that will be learned from this pilot study.

Statistical Analysis Plan:

Statistical analysis is expected to be completed within 6 months of the last study visit of the last enrolled subject. Analysis will be conducted with an intention to treat approach. We will aim to recruit up to 40 pregnant subjects and plan for a 20% drop-out rate (n=8) to have 32 subjects complete the study. We aim to enroll up to 40 followers, but as their participation will be not be obligatory outcomes will not depend on their enrollment. As this is a pilot-study and has no formal power, calculations will be performed for the primary or secondary endpoints.

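### The pooled no-CGM arm mixes two selection rules: chart-review controls are chosen on CGM non-use over the whole pregnancy, prospective women on their status when pregnancy is confirmed

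*Combined protocol and SAP*

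**What the plan says.** **Prospective Group 3.** The opening study summary assigns by stated preference: "individuals who do not want to wear a CGM will be stratified to Group 3". The schedule of events for the treatment groups fixes the time: "when pregnancy is confirmed subjects will be stratified to Group 1, 2, or 3".

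**Chart-review Group 3.** The Control Arm section describes women pregnant around or before enrollment "who did not use a CGM device throughout their pregnancies". For the same women it lists "CGM downloads (if applicable) for the most immediate pre-conception visit, all pregnancy visits", and the post-partum visit as well. They complete no questionnaires.

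**Pooling.** Under the treatment groups heading: "we will include pregnant no CGM users identified through a retrospective chart review into the no CGM arm of the study". Under subjects per treatment arm: "We will include up to 30 additional women in Group 3 identified through a retrospective chart review", beside an anticipated 10 prospective women in that group.

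**Analysis.** The SAP states: "Analysis will be conducted with an intention to treat approach". It does not define this for a non-randomized study. It says nothing about a Group 3 woman who starts CGM, and it does not separate the two control sources.

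**The concern.** Eligibility of a chart-review control depends on what she did during the period in which her outcomes are measured. A woman who began pregnancy without CGM and started it partway through is not admitted. A prospective woman with the same history has already been classified, and intention to treat as usually understood keeps her.

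This would be harmless if starting CGM were unrelated to glucose control, but there is reason to doubt that. The section on risks and justification says the national diabetes association "recommends CGM use during pregnancy for high-risk individuals", and that many pregnant patients at the center use CGM in usual care. Women who start during pregnancy may therefore differ from those who never do. Leaving them out of one control source and not the other can distort the comparison of Groups 1 and 2 with Group 3 on A1C and SMBG-based variability. The planned mixed models allow for missing measurements on women in the data set. They cannot restore women who were never abstracted.

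**Working it through.** **1. The plan's own figures.** 40 × 0.20 = 8 drop-outs; 40 − 8 = 32 completers; 10 + 20 + 10 = 40 prospective women. All reproduce. There is no power-based sample size to check.

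**2. The two rules side by side.**

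| | Chart-review controls | Prospective Group 3 |
|---|---|---|
| Basis of classification | CGM non-use across the pregnancy | Does not want a CGM |
| When it is known | End of pregnancy | When pregnancy is confirmed |
| Starts CGM after entry | Not admitted | Kept, if intention to treat has its ordinary meaning; not written out |

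Take a woman without CGM at week 10 who starts at week 18. She is in the arm if enrolled prospectively and out of it if found in the charts.

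**3. Share of the arm affected.** 30 / (10 + 30) = 75%. If 2 of the 10 prospective women drop out, 30 / (8 + 30) = 79%.

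**4. Would a starter occur at all?** The documents give no rate. Let s be the assumed probability that a woman without CGM at entry starts later. The chance of at least one starter among 10 prospective women is 1 − (1 − s)^10:

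- s = 5%: 40%
- s = 10%: 65%
- s = 20%: 89%
- s = 30%: 97%

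**5. Illustrative size for A1C.** Let D be the mean A1C of starters minus that of never-starters, also an assumption. Keeping starters gives a chart-review mean of m + s × D, where m is the never-starter mean. Excluding them gives m. Relative to keeping starters in both sources, the pooled mean therefore moves by 0.75 × s × D in absolute size:

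- s = 5%, D = 0.3: 0.75 × 0.05 × 0.3 = 0.011 points; 0.011 / 0.3 = 4%
- s = 10%, D = 0.5: 0.75 × 0.10 × 0.5 = 0.038 points; 0.038 / 0.3 = 13%
- s = 20%, D = 1.0: 0.75 × 0.20 × 1.0 = 0.150 points; 0.150 / 0.3 = 50%
- s = 30%, D = 1.0: 0.75 × 0.30 × 1.0 = 0.225 points; 0.225 / 0.3 = 75%

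The divisor is the possible 0.3-point A1C reduction named in the SAP. If starters have the higher A1C, excluding them lowers the control mean. If they have the lower A1C, for example because they are more motivated, it raises it.

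**6. What this figure is not.** It is a shift in level. The SAP also compares outcomes within women over time and A1C across trimesters from baseline. Any part of D already present at baseline largely cancels in a change contrast, so only a difference in trajectory would remain. No comparable figure can be formed for glucose variability, because the documents give no scale for it.

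**The case against.** Several points on the other side have weight.

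- **Only one rule is written.** A reader might infer that the plan states two opposite rules. It does not. Retention of prospective starters follows from one generic intention-to-treat sentence, in a design where the term is not defined. This stands. The mismatch rests on the ordinary meaning of that sentence, together with the absence of any switching rule.
- **Starters may be few.** Prospective Group 3 women have declined an offered CGM, and the Control Arm section says they lack access to the Dexcom G4. This may lower the rate. It does not cover other CGM sources, and the recruitment section itself mentions non-Dexcom CGM. Nor does it say what happens to a woman who starts.
- **Part-time users.** The Control Arm wording could be read as not using CGM for the entire pregnancy, which would admit part-time users as controls. The documents do not favor this. The study population, treatment groups and data collection sections all describe these women as not using CGM. Downloads marked as if applicable are a stock list item and also cover visits outside pregnancy. That reading would also come closer to intention to treat for mid-pregnancy starters, so it cannot be said that every reading conflicts with the prospective rule. The wording should still be made exact.
- **Never-users are the stated comparison.** The Research Design section describes the comparison group as women not using CGM in pregnancy. That supports reporting a never-user contrast. It does not justify choosing controls on later exposure in one source only, because women can be included at the first visit and censored at CGM start.
- **It is a non-randomized pilot.** The protocol admits this weakness, but this mismatch is avoidable without randomization.

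**Conclusion.** The inconsistency is real and worth correcting. About 75% of the planned no-CGM arm is selected on a status known only after follow-up; the remainder is classified when pregnancy is confirmed, and no section reconciles the two. This can bias the A1C and SMBG-variability comparisons with Group 3.

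A reader might go further and infer that the control arm will look too good and hide a benefit of CGM. The documents do not support a direction. They say CGM is recommended for high-risk women, not that such women start it mid-pregnancy rather than before the first visit. The 0.01 to 0.23 point range rests wholly on assumed values of s and D, can take either sign, and overstates the effect on any change-from-baseline contrast. A1C is a secondary endpoint. Of the two primary endpoints, hypoglycemia fear is unaffected, since chart-review women complete no questionnaires; glucose variability measured by SMBG is exposed.

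**What to change.** 1. In the Control Arm section, define chart-review controls as women not using CGM at their first pregnancy visit at 13 weeks or less. This aligns their classification with that of the prospective women.
2. Record the date of any later CGM start, from the chart data already to be collected and in the same way for prospective Group 3.
3. State in the SAP that both control sources are analyzed as classified at that visit, whether or not CGM is started later.
4. Add one sensitivity analysis, applied identically to both sources, that censors follow-up at CGM start or restricts to never-users. Censoring keeps the starters' measurements up to that date. Either version addresses the comparison described in the Research Design section.

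The cost is one reworded criterion, one date field, a sentence on retention and one extra analysis. No woman's care changes. The downside is slight dilution of the main contrast, because some controls will have used CGM for part of the pregnancy.

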CGM data will be analyzed for mean blood glucose values, time spent in hyperglycemic (>240, >300mg/dl) and hypoglycemic (<50, <70, <80 mg/dl) ranges and various indices of glycemic variability. Laboratory analysis for A1C will be performed at baseline, monthly thereafter during the pregnancy, and post-partum. Routine blood tests will be performed in all subjects in each trimester (see Table 1).

Primary outcomes will be:

- 1) Glucose variability as measured by glucose excursions from self-monitoring blood glucose (SMBG) data through log books and downloads as well as CGM downloads and various indices [J-index, mean amplitude of glycemic excursion (MAGE), high blood glucose index (HBGI), low blood glucose index (LBGI)] from CGM downloads.
- 2) Changes detected by the hypoglycemia fear questionnaire.

Secondary outcomes will be:

- 1) How CGM alone and CGM with Share™ usage affect A1C compared to no CGM use,
- 2) Progression of diabetes complications (retinopathy, nephropathy),
- 3) Maternal and fetal outcomes (eclampsia/pre-eclampsia, live birth rates, birth weight, neonatal hypoglycemia, and other similar measures).

Introduction:

Among the US population, 29.1 million people (9.3%) have diabetes (1). Pre-existing diabetes has to be managed very carefully throughout pregnancy to optimize maternal and fetal outcomes (2). Among women

with T1DM who are pregnant, the tools that we have to regulate maternal glucose control include multiple daily injections (MDI), continuous subcutaneous insulin infusion therapy (CSII) also known as insulin pump therapy, and for high-risk individuals continuous glucose monitoring (CGM) (2). CGM use in pregnancy has been shown to be safe, to reduce the frequency of severe hypoglycemia, and to improve A1C values (3-6). Sensor-augmented pump therapy with CGM use continuously was shown to lower A1C more than intermittent use in pregnant women with T1DM (7). However, few studies have measured changes in glucose variability that occur with CGM use during pregnancy and no studies have evaluated how tools that allow family and friends (followers) to access glucose trends affect outcomes during pregnancy.

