The primary endpoints are glucose variability and changes detected by hypoglycemic fear survey. We will measure indices of glucose variability (mean glucose \pm SD, % of glucose within/above/below target ranges, J Index, High Blood Glucose Index [HBGI], Low Blood Glucose Index [LBGI], Mean Amplitude of Glycemic Excursions [MAGE], CONGA_n) throughout pregnancy using the SMBG 7-point profiles for one week taken once per trimester. Hypoglycemic fear survey results will be assessed once monthly over the pregnancy. We will compare outcomes within individuals over time and between individuals of the different study arms. We will test whether outcomes differ between women using Dexcom alone and women using Dexcom with Share™ using interaction terms, and will stratify analyses if differences by group are greater than 10 mg/dL in mean glucose levels are detected. Since SMBG logs will be taken at multiple time points over the pregnancy and since CGMs will be worn continuously for the duration of each pregnancy, linear mixed models will be used to assess changes in outcome measures (GV, time spent in target below or above target) over time in each trimester of pregnancy. We will use linear mixed models to assess changes in the hypoglycemic fear survey in each month of the pregnancy. Secondary endpoints include A1C differences among study arms. Improvement in glycemic variability parameters with a possible reduction of A1C by 0.3%, measured as the difference of the mean A1C laboratory values of the arms of the study between baseline (0-3 months, first trimester), second trimester (3-6 months), and third trimester (6 to 9 months). Mixed models account for missing data, allow for an unstructured covariance matrix for repeated measures, and account for inter-subjects correlation of measurements. Secondary outcomes will be used

in the same mixed models. Differences in frequency of low alert glucose rates, high alert glucose rates, and interventions for low or high glucose values among the followers for each study arm will be analyzed with student t-tests. A p-value < 0.05 will be considered significant, and we will perform statistical analyses with SAS software (version 9.3, SAS Institute, Cary NC).

Publication Strategy:

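### The primary glucose endpoint has two conflicting data sources, and the added chart-review controls have no stated route into it and cannot enter the fear-survey endpoint

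*Combined protocol and SAP*

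**What the plan says.** **Glucose source.** The primary outcomes list in the opening summary has two parts. Excursions come from "glucose excursions from self-monitoring blood glucose (SMBG) data through log books and downloads as well as CGM downloads". The indices (J-index, MAGE, HBGI and LBGI) come from one source only: "low blood glucose index (LBGI)] from CGM downloads". The Statistical Analysis Plan (SAP) names the same indices, adds mean and SD, percentages in, above and below range and CONGA_n, and measures them "throughout pregnancy using the SMBG 7-point profiles for one week taken once per trimester". A few sentences later it cites the SMBG logs and adds "since CGMs will be worn continuously for the duration of each pregnancy, linear mixed models will be used to assess changes in outcome measures", those measures being glucose variability and time in, below or above target. It plans comparisons between the study arms.

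**Who has which data.** Visits 3 through 13 ask all prospective subjects for the 7-point week once per trimester, recorded on the Appendix D form, and collect meter downloads at least monthly. The Control Arm section describes chart-review women as having used no CGM through pregnancy. From their records it abstracts, among other items, "glucose meter downloads, insulin pump downloads (if applicable), and CGM downloads (if applicable".

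**Fear survey.** It is the second primary endpoint. The opening summary hypothesizes that Share will "decrease hypoglycemia fear and the frequency of severe hypoglycemic episodes compared to CGM use alone in pregnancy or not using CGM use in pregnancy". The Control Arm section says of the added controls: "Subjects identified through the retrospective chart review will not have filled out any of our questionnaires (baseline, hypoglycemic fear, and postpartum questionnaires", and that they will not be asked to.

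**Numbers.** The plan anticipates 10, 20 and 10 women in Groups 1, 2 and 3, says group sizes cannot be predicted, and adds up to 30 chart-review women to Group 3 because most women are expected to choose CGM.

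**The concern.** A primary endpoint defined from CGM downloads cannot be computed in the arm without CGM. The SAP's fingerstick definition can be, but it does not replace the other one, and the SAP itself then brings CGM into the same models. An analyst could follow the text and use CGM values in Groups 1 and 2 and fingerstick values in Group 3. Arm and instrument would then be inseparable, and a measurement difference could be reported as an effect of CGM.

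The chart-review women were added to strengthen the no-CGM arm. They have neither CGM data nor the requested profile week, so the SAP as written does not say how they contribute to glucose variability. They contribute nothing to the fear survey. A reader who sees a Group 3 of up to 40 could misjudge how much information lies behind either primary comparison.

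**Working it through.** **1. The plan's own figures.** 10 + 20 + 10 = 40 women. With 20% drop-out, 40 × 0.80 = 32, as the SAP states. Spread equally over the groups (an assumption), 10/20/10 becomes 8/16/8.

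**2. Which source exists for whom.**

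| Source | Groups 1 and 2 | Group 3, prospective | Group 3, chart review |
|---|---|---|---|
| CGM downloads (primary outcomes list) | yes | no | no |
| Requested 7-point week (SAP) | yes | yes | no |
| Meter downloads | yes | yes | yes, where archived |
| Fear survey | yes | yes | no |

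The requested week is common to the prospective arms. Only meter downloads are common to everyone, and the SAP does not name them as the source of the indices.

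**3. Why the instrument matters.** In the profile, 3 of 7 points (43%) are 2-hour post-meal values and none falls between bedtime and fasting. CGM covers the whole day. The same index from the two sources does not measure the same thing in the same woman. The documents give no data on the size of the difference.

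**4. Share of Group 3 from chart review, if all 30 are found.** 30/(10 + 30) = 75%. With 8 prospective completers, 30/38 = 79%. With only 5 prospective controls (illustrative), 30/35 = 86%.

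**5. Precision of the fear-survey comparison, Group 2 versus Group 3.** The documents give no SD, so results are in SD units. Half-width of the 95% interval = t(0.975, n1 + n2 − 2) × √(1/n1 + 1/n2), for a single time point, equal SDs and no adjustment.

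| Group 2 vs Group 3 | Calculation | Half-width |
|---|---|---|
| 20 vs 10 (all enrolled) | 2.048 × 0.387 | 0.79 SD |
| 16 vs 8 (completers) | 2.074 × 0.433 | 0.90 SD |
| 16 vs 6 | 2.086 × 0.479 | 1.00 SD |
| 16 vs 4 | 2.101 × 0.559 | 1.17 SD |
| 16 vs 2 | 2.120 × 0.750 | 1.59 SD |

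The last three rows use an assumed range, because the plan expects few women to decline CGM.

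**6. What a stated meter route could add for glucose endpoints.** Start from 16 vs 8 (0.90 SD). With 10, 20 or 30 usable chart-review records, the half-width for 16 vs 18 is 2.037 × 0.344 = 0.70; for 16 vs 28 it is 2.018 × 0.313 = 0.63; for 16 vs 38 it is 2.007 × 0.298 = 0.60 SD. This is a gain in precision only. It does not address bias from historical controls.

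**The case against.** **The SAP already sets a common source.** This is largely right for prospective women: the SAP names the 7-point profiles, and all prospective subjects are asked for them. The CGM sentence can be read as explaining why repeated-measures models are used. A reader might infer that the plan intends to compare CGM values with fingerstick values across arms. No sentence says so. What stands is that the primary outcomes list assigns the same indices to CGM, and that the SAP brings CGM into the models without a rule.

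**Chart-review women could still contribute glucose data.** A reader might conclude that they cannot. That goes too far. The outcomes list accepts meter downloads for excursions, the Control Arm section abstracts them, and the Visit 2 text describes seven daily tests as standard of care. Profiles might be rebuilt from meters. The missing route is an inference from the SAP's silence.

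**The fear-survey gap is disclosed.** It is, and no passage claims that these women enter that endpoint. The SAP's remark that mixed models account for missing data does not help: a woman with no score at any visit adds nothing to that model. But no wrong result follows either, so a reporting note is enough. The fear hypothesis against no CGM concerns Share, so only Group 2 versus Group 3 is sized above.

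**Other readings to avoid.** The SAP "will stratify analyses if differences by group are greater than 10 mg/dL in mean glucose levels". A reader might use that figure to judge the gap between instruments, but it belongs to the comparison of Dexcom alone with Dexcom plus Share. Nor do the half-widths show a missed power target: the SAP says that this pilot has no formal power.

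**Conclusion.** The point holds and should be fixed. The two definitions of a primary endpoint conflict, one of them cannot be computed without CGM, and the other does not reach the added controls. Confounding of arm with instrument is possible under the text; it is not stated as planned. The conflict is not confined to comparisons with no CGM. It also leaves open which source serves Group 1 versus Group 2 and change within a woman.

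At the anticipated numbers, 75% of Group 3 would lack a stated route into the variability endpoint, and more if fewer than 10 prospective controls enrol or complete. The fear-survey comparison with no CGM rests on about 10 enrolled or 8 completing controls, possibly fewer. Its half-width is 0.79 to 0.90 SD, rising to 1.00 to 1.59 SD with 6 down to 2 completing controls.

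These figures assume equal drop-out across groups, a single time point, equal SDs and no adjustment. The planned mixed models also use partial data, so the absolute values are indicative.

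**What to change.** 1. Reconcile the primary outcomes list with the SAP. State that every glucose comparison with no CGM uses fingerstick data derived the same way in all arms. Make the 7-point profile in prospectively enrolled women, within the Appendix D gestational windows (8 to 12, 20 to 24 and 32 to 36 weeks), the main analysis.
2. Bring chart-review women in through a second analysis that uses meter downloads in all arms, cut to the same gestational windows and to pre-set time-of-day windows. Report readings per woman per day by arm.
3. Use CGM-download indices and CGM time in range only for Group 1 versus Group 2 and for change within a woman. Report non-Dexcom sensors in Group 1, since the recruitment section places those users there.
4. Label the fear-survey comparison with no CGM as prospective-only and give its n.

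Optional: the chart-abstraction list names no birth or neonatal fields. The post-partum visit is abstracted and may hold some, so listing the wanted fields and reporting how many are missing would help.

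The cost is SAP wording, some extra processing of downloads already collected and, if the optional step is taken, a few abstraction fields; no extra women or visits are needed. The limits should be stated. Fingersticks miss most overnight glucose. Checks prompted by CGM may over-sample lows and highs in Groups 1 and 2, which is why meter downloads should not be the main source. Archived downloads may be incomplete. Historical controls bring selection and calendar-time differences that narrower intervals do not remove.
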